February 6, 2025

Signature & Date

2 List of Abbreviations

- CI: Confidence Interval
- CRP: C-reactive protein
- GBS: Group B streptococcus
- ITT: Intention-To-Treat
- PP: Per Protocol
- SAE: Serious Adverse Event
- SAP: Statistical Analysis Plan

3 Introduction

This document is the statistical analysis plan (SAP) for an open label, investigator-initiated, parallel group, 1:1 randomized, multicenter, non-inferiority clinical trial of “individualized” versus “standard” duration of antibiotic treatment for culture negative early-onset infection in term newborns. The individualized treatment duration is based on structured clinical assessment of symptoms and level of C-reactive protein (CRP). The individualized treatment duration can be as short as two days while the standard treatment duration is seven days. It is hypothesized that an individualized treatment duration will shorten the duration of antibiotic therapy in newborns with early onset infection with no or very limited increase in the risk of relapse.

The trial recruited newborns from all Departments of Neonatology in Denmark except one (17 out of 18). Stratified randomization was planned 36 to 48 hours after the treatment started using permuted blocks of size six, stratified on maximum CRP level within the last 48h above or below 90 mg/l. Patient accrual started in Spring 2022 and was anticipated to stop in January 2025, after inclusion of 488 newborns.

The changes to the protocol-planned analyses are summarized in Section 12. We do not consider them as major changes and the rationale for each of them is provided.

4 Objectives, Endpoints, and Estimands

4.1 Primary objectives, endpoints and estimands

There are two co-primary objectives and therefore two co-primary outcomes in this trial.

The first objective is to show that an “individualized” antibiotic treatment duration is non-inferior to a “standard” treatment duration for treating culture negative early-onset infection in term newborns, with respect to the risk of readmission due to bacterial infection. By non-inferior, we mean that the risk of readmission due to bacterial infection within 28 days is not larger with the “individualized” duration than with the “standard” duration, by more than the pre-specified non-inferiority margin of 4%. The rationale for choosing this margin is provided in Section 4.1.2.

The second objective is to show that the “individualized” antibiotic treatment duration leads to less antibiotics days than the “standard” treatment duration. More specifically, the second objective is to show superiority of the “individualized” treatment duration with respect to the

median of the total duration of antibiotics use within 28 days from treatment start. Although the initial treatment duration will systematically be shorter using the “individualized” duration, relapses can happen, leading to new initiations of antibiotic treatment. Hence it remains to confirm that the median of the total duration of treatment within 28 days is shorter using the “individualized” initial duration than using the “standard” initial duration. This is precisely the second objective.

The two treatment strategies (interventions) being investigated for initial treatment are detailed below. Of note, the two strategies below are defined for newborns who have already received 36 to 48 hours of treatment, hence none can lead to a treatment discontinuation before a newborn has received at least 36 hours of antibiotic treatment.

- **Experimental (“individualized”):** discontinuation of antibiotics when both of the following two criteria are fulfilled:

1. The infant has been 24 hours without clinical symptoms of infection, after systematic clinical evaluation by a neonatologist. The clinical symptoms that are considered are those specified in Table 1 below. They are those of the “easy-to-use” scoring system originally published by Stocker et al. [24], up to minor modifications.
2. CRP is declining and $\leq 30 \text{ mg/l}$.

We define CRP as declining if the current value is less than the most recent previous value. CRP is assessed regularly¹ until the condition of the previous item is fulfilled and once every 24-48 hours afterwards.

- **Control (“standard”):** discontinuation of antibiotics after the same standard duration for all infants. This standard duration is set to seven days in nearly all participating Departments (and in all of the largest), but it is five days in a few². In the extremely unlikely case where a child would still have clinical symptoms of infection by the end of the standard duration, treatment will be prolonged as needed. Hence, using a “standard” treatment duration strategy cannot result in a shorter initial treatment duration than using the “individualized” treatment duration strategy.

1	Tachypnea, apnoea, use of respiratory support or oxygen supplementation
2	Tachycardia
3	Arterial hypotension
4	Hypothermia or hyperthermia
5	Seizure, floppy infant, irritability, or lethargy
6	Feeding insufficiency, vomiting, or ileus

Table 1: Clinical symptoms (slightly modified from Stocker et al. [24, Fig. 1]).

4.1.1 Readmission due to bacterial infection

The first co-primary outcome (**P1**) is hospital readmission due to bacterial infection (or death, although none is expected), within 28 days after treatment started. Specifically, hospital readmission due to bacterial infection is defined as hospital readmission that fulfills all of the following:

¹By regularly we mean every 18 to 48h, typically every 24h, approximately.

²Specifically, seven days in 15 out of 17 departments, including all of the largest; five days in two departments.

- ≥ 1 clinical symptom(s), among those listed in Table 1
- CRP during readmission > 10 mg/l
- ≥ 72 hours of antibiotic treatment received following readmission

Note that there is no minimum time for the time to readmission as we define and record it. A newborn can be readmitted as early as the day of discharge or the following day.

The first co-primary clinical question of interest is: *“Is the risk of hospital readmission due to bacterial infection within 28 days after the start of treatment not more than 4% higher when using the individualized treatment duration than when using the standard duration of seven days, regardless of initiation of any additional interventions during the follow-up, when needed to ensure good clinical care?”*

To answer this question, we will use two co-primary estimands. The first corresponds to an **“intention-to-treat estimand”** and is described by the following attributes:

- Population: infants diagnosed with a probable or possible infection within 0-72 hours from birth according to a structured infection risk assessment, who have received 36 to 48h of antibiotic treatment and no positive blood culture result so far; infants are born with gestational age ≥ 35 weeks and weight ≥ 2000 g.
- Endpoint: hospital readmission due to bacterial infection (as defined above; or death) within the first 28 days after treatment initiation.
- Treatment: The investigational interventions (“individualized” vs “standard”, as defined above) regardless of any subsequent treatment decision or intervention during the follow-up needed to ensure good clinical care and regardless of adherence (“treatment policy strategy”, see [15]).
- The intercurrent event “any subsequent treatment decision or intervention” is addressed by the treatment condition of interest attribute (“treatment policy strategy”, see [15]). The intercurrent event “death within 28 days” is addressed by the endpoint definition (“composite variable strategy”, see [15]). The intercurrent event adherence to the investigational intervention (i.e., “the patient actually received the treatment according to the randomized treatment strategy”, i.e., neither shorter nor longer duration than randomized duration) is also addressed by the treatment condition of interest attribute (“treatment policy strategy”, see [15]). There are no other relevant intercurrent events anticipated.
- Population-level summary: Difference in risk between treatment conditions.

The second co-primary estimand corresponds to a **“per protocol estimand”** and only differs from the previous estimand for these attributes:

- Treatment: The investigational interventions (“individualized” vs “standard”, as defined above) regardless of any subsequent treatment decision or intervention during the follow-up needed to ensure good clinical care (“treatment policy strategy”, see [15]). Unlike with the previous estimand, here adherence to the randomized treatment strategy is required (“hypothetical strategy”, see [15]).

- The intercurrent event “any subsequent treatment decision or intervention” is addressed by the treatment condition of interest attribute (“treatment policy strategy”, see [15]). The intercurrent event “death within 28 days” is addressed by the endpoint definition (“composite variable strategy”, see [15]). Another possible intercurrent is “the patient did not receive the randomized treatment strategy” (e.g., stopped treatment prematurely or continued too long). A scenario is envisaged in which this does not occur (“hypothetical strategy”, see [15]). There are no other relevant intercurrent events anticipated.

Rationale for these co-primary estimands. As we expect a very small proportion of non adherence (< 5%), the two estimands are considered very similar. However, in general, it is often considered “advantageous to demonstrate a lack of sensitivity of the principal trial results to alternative choices of the set of subjects analysed” [14, Sec 5.2.3]. An important advantage of the “Intention-To-Treat” estimand over the “Per Protocol” estimand is that it can be estimated without bias under weaker assumptions, because of randomization [11]. However, the “Intention-To-Treat” estimand interpretation depends on the level of adherence and poor adherence will generally make the two arms more similar, hence facilitating demonstration of non-inferiority. Specifically, in our trial, a non negligible proportion of newborns randomized to “short” receiving longer treatment duration than according to the “short” treatment strategy could make the two arms more similar than they should, according to the randomization. The interpretation of the “per-protocol” estimand does not depend on the level of adherence, but inference for this estimand inevitably relies a few additional assumptions (e.g. unmeasured confounding), which might be questionable [13, 2]. Consequently some guidelines recommend that both should have equal importance [5]. See e.g., Evans and Ting [8, Sec. 8.3.2] for similar remarks.

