4.1.3 Total duration of antibiotics use within 28 days

The second co-primary outcome (**P2**) is total duration of antibiotics use (in hours) within 28 days from treatment start.

Precisely, total duration is defined as the sum of the durations of each treatment episode, within

28 days. Each duration is computed from the time and day of start and end of treatment³, registered by the clinicians and nurses. The start time and date are observed and registered accordingly. For end of treatment, what is registered corresponds to the time and day at which the prescribed treatment expires. The corresponding doses are given to the parents before discharge. No data are available on whether the doses were actually received by the newborn, but unlike with some populations of adults patients, we can reasonably expect perfect or nearly perfect adherence/compliance here, with newborns and their caring parents. Note also that the treatment cannot be prolonged by the parents without the consent of the clinicians, since the parents only receive the remainder number of doses, not a bottle.

The second co-primary clinical question of interest is:

"Is the median total duration of antibiotics use within 28 days after the start of treatment lower when using the individualized treatment duration than when using the standard duration of seven days, regardless of initiation of any additional interventions during the follow-up, when needed to ensure good clinical care?"

We consider that both the corresponding "intention-to-treat" (ITT) and the "Per protocol" (PP) estimands are relevant, as for the first co-primary outcome. Accordingly, the corresponding co-primary estimands are defined as the estimands of Section 4.1, except for the endpoint attributes, which are now defined by **P2** instead of **P1** and the population-level summary attributes, which are now defined by a difference in medians. Although no death is expected, note that here the intercurrent "death" is still addressed by the endpoint: antibiotics use is by definition zero after death ("composite variable strategy", see [15]).

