10.2.6 Oral and intravenous antibiotic treatment

For each arm, we will report how many newborns switch from intravenous to oral antibiotic treatment and when. For completeness and to document the timing of the switches, cumulative incidence plots, per arm, will be provided. We will also report the median (if more than half indeed switch) or another quantile of the time to switch (if less than half switch), per arm, for completeness. It is expected that most switches happen close to 48 hours after treatment started.

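### P1's 72-hour antibiotic criterion does not exclude the rest of the index course, which may add control-arm events and favour non-inferiority

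*SAP*

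**What the plan says.** SAP Section 4.1.1 defines P1 as a readmission "within 28 days after treatment started" that meets all of three conditions: "≥ 1 clinical symptom(s), among those listed in Table 1", "CRP during readmission > 10 mg/l" and "≥ 72 hours of antibiotic treatment received following readmission". It adds "Note that there is no minimum time for the time to readmission as we define and record it", and then "A newborn can be readmitted as early as the day of discharge or the following day". Nothing requires the antibiotics to be newly started, changed or prolonged, and nothing sets aside what is left of the index course. S1 takes over the same definition over 100 days (Section 4.2).

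Other sections show that infants can be at home while still on the index course. Section 4.1.3 says of the prescribed treatment that "The corresponding doses are given to the parents before discharge". Section 10.2.6, on the change from intravenous to oral treatment, says "It is expected that most switches happen close to 48 hours after treatment started".

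The standard course is seven days in 15 of 17 departments and five days in two (Section 4.1.1, footnote 2). The individualized course ends when the symptom and CRP criteria are met. Section 12 puts it at between 2 and 7 days.

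Section 12 also explains why the P1 window now runs from treatment start instead of for 21 days after treatment stop. It calls the change conservative and says it can only add events in the experimental arm.

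**The concern.** Whether the 72-hour condition is met can depend on the randomized duration itself. Take two infants readmitted at hour 80 with poor feeding and a CRP still above 10 mg/l. The standard-arm infant has 168 − 80 = 88 hours of assigned treatment left and meets the condition by finishing it. The individualized infant whose course has already ended meets it only if a new course of at least 72 hours is given. The same readmission can then count in one arm and not in the other.

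The extra events would fall mainly in control. They would lower π₁ − π₀ and make non-inferiority easier to declare. The ITT and PP analyses share the definition, so neither protects the other. No planned analysis changes the count: Section 7.1.1 varies only the outcomes of infants excluded from the PP set, and Sections 10.1.1 and 10.1.4 describe readmissions and their timing.

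The direction claimed in Section 12 is also incomplete. A window that opens at treatment start takes in readmissions during the index course. A window that opens at treatment stop, read literally, does not. Standard-arm infants spend longer on the index course, so the change can add control events too.

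**Working it through.** **1. When the index course alone supplies 72 hours.** Inputs are the course lengths and the 72-hour threshold in Section 4.1.1. Hours left at readmission time t are L − t, and the condition is met when L − t ≥ 72.
- Seven-day course: L = 168, so t ≤ 96.
- Five-day course: L = 120, so t ≤ 48. With most oral switches expected near 48 hours, this window is practically empty.

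Between hours 96 and 168 on a seven-day course, the remainder is below 72 hours. An extension, which is a treatment decision, is then needed.

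**2. The plan's own figures.** Inputs from Section 11: risks 1.5% and 1%, margin 4%, one-sided 2.5%.
- The normal approximation at 207 per arm, Φ(0.035/√(0.015·0.985/207 + 0.01·0.99/207) − 1.96), gives 89.4% (stated as about 90%).
- 207/(1 − 0.15) rounds up to 244, as stated.
- Full enumeration of two binomials with the Miettinen-Nurminen score test at 207 per arm gives 67.3%, as stated in Section 11.2. The same method gives 80.0% at 244 per arm.

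**3. What one more control event does.** Miettinen-Nurminen two-sided 95% upper limits, experimental vs control events:

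| Per arm | Before | Upper limit | One more in control | Upper limit | Verdict changes? |
|---|---|---|---|---|---|
| 244 | 4 vs 0 | 4.14% | 4 vs 1 | 3.78% | yes |
| 244 | 5 vs 1 | 4.35% | 5 vs 2 | 3.99% | yes |
| 244 | 3 vs 0 | 3.56% | 3 vs 1 | 3.19% | no |
| 244 | 4 vs 2 | 3.42% | 4 vs 3 | 3.06% | no |
| 207 | 3 vs 0 | 4.18% | 3 vs 1 | 3.75% | yes |
| 207 | 4 vs 2 | 4.02% | 4 vs 3 | 3.59% | yes |
| 207 | 3 vs 1 | 3.75% | 3 vs 2 | 3.32% | no |

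Section 11.2 expects 3.6 and 2.4 events at 244 per arm, so pairs that flip and pairs that do not are both within reach.

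**4. Effect on error rate and power.** The SAP gives no rate for such readmissions, so the added control risk is an assumed range. The middle columns give the probability of declaring non-inferiority when the true risks are 5% vs 1%, that is, on the margin. The last column uses the SAP's planning risks, 1.5% vs 1%.

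| Added control risk | Extra infants (of 244) | 5% vs 1%, 244 per arm | 5% vs 1%, 207 per arm | 1.5% vs 1%, 207 per arm |
|---|---|---|---|---|
| 0 | 0 | 2.0% | 1.7% | 67.3% |
| 0.25% | 0.6 | 2.8% | 2.5% | 72.2% |
| 0.5% | 1.2 | 4.0% | 3.5% | 76.6% |
| 1% | 2.4 | 7.2% | 6.2% | 83.8% |

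The last row adds as much risk as the whole control risk assumed in Section 11.1. It is an upper bound for illustration, not a forecast.

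**The case against.** The strongest reply has four parts.

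- **The SAP is silent on the point.** A reader might infer that P1 counts the leftover course. The documents do not support that: Section 4.1.1 neither counts nor excludes it. The 72-hour element comes from the protocol (Section 12, item 1), which is not at hand and may say how the hours are counted. This stands. The defect is a missing rule.
- **The other conditions still apply.** A reader might infer that an early control readmission becomes an event automatically. It does not, because a Table 1 symptom and CRP above 10 mg/l are also required. An infant who meets both while on antibiotics may be a genuine treatment failure. This stands, but these conditions may filter weakly so early: CRP can still be raised from the index illness, and the individualized rule itself allows stopping at values up to 30 mg/l.
- **The effect is partial.** The window needs discharge and return by hour 96, and the SAP gives the time of the oral switch, not of discharge. Individualized infants still on treatment can also have doses left. This limits the size and means the effect is not exclusive to control. The remainder is still generally longer in control, so the direction is unchanged.
- **The events will be visible.** Sections 10.1.1 and 10.1.4 report each readmission and its timing. A reader could then identify on-course events, but the P1 count and its confidence limit would not change.

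**Conclusion.** The point holds as an unresolved counting rule that can act differently by arm, in the direction that favours non-inferiority. It rests on the literal wording of the third condition, on discharge with doses remaining, and on seven-day courses. It hardly applies in the two five-day departments.

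Its size cannot be estimated from the document. The calculations show sensitivity: a single reclassified control event changes the verdict when counts lie near the margin, and otherwise does not. A reader might infer that the trial is biased by a known amount, or that one such event always decides it. Neither is supported, because no frequency is given and several plausible pairs keep their verdict.

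The statement in Section 12 that the window change can only add experimental-arm events is too strong, because it leaves out control readmissions during the index course. Severity: should be fixed, not a must-fix.

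**What to change.** Keep the P1 definition and make three additions.

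1. **Sensitivity analysis of P1 and S1, ITT and PP**, with the same Miettinen-Nurminen interval, compared with the 4% margin for P1. A readmission during the index course counts only if antibiotics were newly started, changed or extended because of it. Unchanged completion of the index course does not count. The rule is identical in both arms and is fixed before results by arm are seen.
2. **Section 10.1.1:** flag each readmission as on or off the index course.
3. **Section 12:** replace the claim that the change can only add experimental-arm events with one that acknowledges on-treatment control readmissions.

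Redefining P1 to count only hours beyond the planned end of the index course would be less sound. Suppose a control infant is readmitted at hour 80 with a true failure and treated to hour 216. That infant receives 136 hours after readmission but only 216 − 168 = 48 hours beyond the planned end, so the event would be missed. An individualized infant already off treatment and given the same 136 hours would count. The sensitivity rule above counts both.

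The cost is a few sentences and re-coding of a handful of readmissions, mostly from the treatment start and end times already extracted for P2. The downside is that the risk difference in the sensitivity analysis may be slightly less favourable.

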4.1.2 Non inferiority margin choice

The rate of relapse after a proven GBS infection has not been extensively studied, but at time of study planning it was estimated to be between 1% and 8%. Further, two epidemiological studies reported recurrent infection in 1% of cases with proven early onset infection [26, 7]. Only very few studies have examined the rate of relapse in babies with culture-negative infection before the present study was initiated, but it was estimated to be between 0.5% and 1%. The non-inferiority margin was set to 4%, thus accepting 4% more recurrence of infection in the intervention group who received an individualized duration of antibiotic treatment. The non-inferiority margin is justified by the follow-up of babies receiving the individualized treatment, with free access to the neonatal department, thus enabling early recognition of a potential relapse and balanced against the benefit associated with a shorter duration of treatment. A shorter duration of treatment reduces the antibiotic-associated gastrointestinal side effects and will, depending on how the antibiotics are administrated, in some cases, also reduce the length of hospital stay. Additionally, if the non-inferiority margin were set lower, it would require a larger sample size, increasing the cost of the study and its duration. This would have challenged the feasibility of the study.

4.1.3 Total duration of antibiotics use within 28 days

The second co-primary outcome (**P2**) is total duration of antibiotics use (in hours) within 28 days from treatment start.

Precisely, total duration is defined as the sum of the durations of each treatment episode, within

28 days. Each duration is computed from the time and day of start and end of treatment³, registered by the clinicians and nurses. The start time and date are observed and registered accordingly. For end of treatment, what is registered corresponds to the time and day at which the prescribed treatment expires. The corresponding doses are given to the parents before discharge. No data are available on whether the doses were actually received by the newborn, but unlike with some populations of adults patients, we can reasonably expect perfect or nearly perfect adherence/compliance here, with newborns and their caring parents. Note also that the treatment cannot be prolonged by the parents without the consent of the clinicians, since the parents only receive the remainder number of doses, not a bottle.

The second co-primary clinical question of interest is:

"Is the median total duration of antibiotics use within 28 days after the start of treatment lower when using the individualized treatment duration than when using the standard duration of seven days, regardless of initiation of any additional interventions during the follow-up, when needed to ensure good clinical care?"

We consider that both the corresponding "intention-to-treat" (ITT) and the "Per protocol" (PP) estimands are relevant, as for the first co-primary outcome. Accordingly, the corresponding co-primary estimands are defined as the estimands of Section 4.1, except for the endpoint attributes, which are now defined by **P2** instead of **P1** and the population-level summary attributes, which are now defined by a difference in medians. Although no death is expected, note that here the intercurrent "death" is still addressed by the endpoint: antibiotics use is by definition zero after death ("composite variable strategy", see [15]).

